6.2.1. Incidence Rate Estimation

To estimate power for this component we first had to estimate the proportion of participants who would be free of the condition at their initial in-person visit during SEARCH 1 and 2. Table 6-1 shows the expected sample sizes available for comparing incidence rates between subgroups under two scenarios: 1) proportion in subgroups are 86% versus 14% (the proportions of T1D and T2D), and 2) proportion in subgroups are 65% versus 35% (the proportions of NHW and all others).

 Table 6-1: Expected Sample Sizes Available for Comparing Incidence Rates between Subgroups

 Under Two scenarios

	Scenario 1		Scena	ario 2		
Outcome (% of participants free of	Subgroup A	Subgroup B	Subgroup A	Subgroup B		
condition at initial SEARCH visit)	(86%)	(14%)	(65%)	(35%)		
	Expected n	Expected number of participants free of outcome at initial visit				
Hypertension (92%)	2504	423	1893	1019		
Obese (bmi-z \ge 95 th %ile) (76%)	2069	349	1564	842		
High LDL (≥ 100) (57%)	1511	262	1173	631		
High ACR (≥30 (90%)	2450	414	1852	997		
Hypoglycemia in last 6 months (91%)	2477	418	1872	1008		
DKA in last 6 months (85%)	2314	391	1749	941		

Using this table we can determine detectable differences for each outcome/group comparison for a variety of plausible scenarios for incidence rates. Table 6-2 illustrates detectable differences assuming a two group continuity corrected chi-square test for a variety of scenarios with alpha=0.05 (2-sided).

Table 6-2. Detectable Differences in Selected Outcomes Assuming a Two-Group Continuity							
Corrected Chi-square Test for a Variety of Scenarios with Alpha=0.05 (2-sided)							
	Scenario 1: Example T1 vs. T2 Scenario 2: NHW vs. Other						
Outcome	Incidence Rate	Detectable Rate	Incidence Rate	Detectable Rate			
	for T1	for T2 (Power)	for NHW	for Other			
				Race/Ethnic			
				Group (Power)			
Hypertension	6%**	10% (80%)	6%**	10% (96%)			
	12%	18% (88%)	12%	17% (95%)			
Obese	5%	10% (90%)	9%	14% (95%)			
	10%	16% (86%)	19%	25% (91%)			
High LDL	23%	32% (84%)	14%	20% (89%)			

Section 6B - Statistical Considerations (P	hase 3 - 12/2010)
Cohort Study	

	33%	43% (85%)	24%	31% (87%)	
High ACR	9%	15% (93%)	5%	8% (86%)	
	19%	26% (87%)	10%	14% (87%)	
Hypoglycemia in last 6 months	11%	17% (90%)	23%	28% (82%)	
	21%	28% (86%)	33%	39% (88%)	
DKA in last 6 months	15%	21% (81%)	9%	13% (87%)	
	25%	32% (80%)	19%	24% (84%)	
** First incidence rate reflects observed incidence rate in SEARCH 1 and 2 for follow-up visits already measured.					

Based on this table, we see, for instance, that there is 90% power to detect a difference between Type 1 and Type 2 participants on their rate of incident obesity if the rate of incident obesity is 5% in the Type 1 group and 10% or higher in the Type 2 group. Likewise, there if the rate of obesity were 9% in the NHW group then there is 95% power to detect a "Other" race/ethnic group rate of 14% or higher. The above calculations should be conservative since when we adjust for participant level characteristics in our models we should reduce variability and increase precision as we estimate the difference in incidence rates between groups.

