Diabetic Nephropathy. The incidence of diabetic end-stage kidney disease (ESKD) in 2007 was more than double that in 1990⁽⁴⁶⁾, with even greater increases among AA and AI populations. Worsening glomerular filtration rate (GFR) carries up to a three-fold risk of cardiovascular event and six-fold risk of death ⁽⁴⁷⁾. Correlates of diabetic kidney disease include glycemic control ^(48, 49), diabetic retinopathy ⁽⁵⁰⁾, blood pressure ^(51, 52) and possibly lipids ^(53, 54), inflammatory and fibrotic markers ^(55 - 57), vitamin D deficiency ^(58, 59) and diagnosis during puberty ⁽⁶⁰⁻⁶⁵⁾; and in T2D, nephropathy has been associated with increased pulse wave velocity ^(66, 67). From SEARCH, the prevalence of elevated urinary albumin-to-creatinine ratio (ACR) was 9.2% in youth with type 1 and 22.2% in type 2 diabetes (p < 0.0001). In multiple logistic regression analysis, female sex, higher A1C and triglyceride values, hypertension, and type of diabetes (T2 versus T1D) were significantly associated with elevated ACR. Adjustment for variables related to insulin resistance (obesity, hypertension, dyslipidemia, and inflammation) attenuated, but did not completely explain, the association of diabetes type with elevated ACR⁽⁶⁸⁾. The SEARCH Cohort Study will provide much needed additional information in a longitudinal design. SEARCH is uniquely positioned to obtain critical information regarding the prevalence and risk factors of diabetic nephropathy across subgroups of diabetes

type and race/ethnicity. Especially important, since so little is known, SEARCH will provide much needed information on early nephropathy in T2D.

Neuropathy. The topic of diabetic neuropathies is complex both due to the diverse clinical manifestations and due to difficulties in measurement methods. Here we focus on chronic distal symmetric polyneuropathy (i.e., peripheral neuropathy) and cardiac autonomic neuropathy.

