4.2.1.2. Risk Factors

Glycemic Control. Studies among children and youth with diabetes generally report a constellation of related socio-demographic factors that are associated with poor glycemic control, including race/ethnicity, socioeconomic status, lower parental educational attainment, parental involvement in diabetes management, and family dynamics $^{(81-87)}$. Similar patterns were observed in SEARCH, both for T1 and T2D youth $^{(11)}$, and may be partly mediated by our observation of worse glycemic control among T1D youth on insulin regimens other than CSII $^{(24)}$. In SEARCH, 17% of youth with T1D (n=3947) and 27% of T2D (n=552) respectively had poor glycemic control (HbA_{1c}> 9.5%). For both T1 and T2D, higher A1c was also associated with higher concentrations of apoB and LDL particle size $^{(88)}$, and elevated ACR $^{(68)}$, suggesting possible links early in the history of diabetes between glycemic control and future risk for both macro- and microvascular disease that require further study.

Cardiovascular (CV) Risk Profile. CV risk factors track from childhood to adulthood $^{(89, 90)}$ and risk factors measured in youth predict adult target organ damage $^{(91-93)}$. Thus, an adverse risk profile among youth with diabetes may magnify the already three-fold excess risk for CV mortality associated with diabetes in adulthood $^{(94)}$. In SEARCH, we found that T1 youth had a prevalence of overweight (22%) that was significantly higher than that of non-diabetic counterparts, and ~ 90% of youth with T2D were overweight or obese $^{(95)}$. The prevalence of metabolic syndrome among SEARCH youth with T1D was 14%, and 92% for youth with T2D $^{(96)}$. Further, among youth with T1D, 11% had elevated apoB, 8% had dense LDL, and 12% had elevated LDL-cholesterol. In contrast, among youth with T2D, 36% had elevated apoB, 36% had dense LDL, but only 23% had elevated LDL-cholesterol. Moreover, the prevalence of elevated blood pressure in youth with type 1 was 5.9%; minority ethnic groups, obese adolescents and youth with poor glycemic control were disproportionately affected. In contrast, 23.7% of adolescents with type 2 diabetes had elevated BP (p<0.0001) $^{(97)}$.

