6.2. POWER ANALYSIS

Based on our calculations from SEARCH 1 and 2 we anticipate that at least 3,288 subjects will participate in the SEARCH Cohort Study in-person visit, and therefore the calculations below use that sample size as the starting value for estimating power and detectable differences.

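### Table 6-1 gives type 2 participants the whole-cohort event-free percentage, so the stated 90% power for incident obesity by diabetes type is probably nearer 56%

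*Protocol*

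**What the plan says.** Section 6B, 6.2 starts from the expectation that "at least 3,288 subjects will participate in the SEARCH Cohort Study in-person visit". In 6.2.1, Table 6-1 lists for each outcome one percentage of participants free of the condition at the first SEARCH visit: 92% for hypertension, 76% for obesity (BMI-z at or above the 95th percentile), 57% for LDL, 90% for ACR, 91% for hypoglycemia and 85% for DKA. It then splits these participants under Scenario 1, where the "proportion in subgroups are 86% versus 14% (the proportions of T1D and T2D". For obesity this gives 2069 type 1 and 349 type 2 participants at risk.

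Table 6-2 converts the counts to power with a "two group continuity corrected chi-square test for a variety of scenarios with alpha=0.05 (2-sided". The text under it picks out obesity: "there is 90% power to detect a difference between Type 1 and Type 2 participants on their rate of incident obesity". The assumed incidence there is 5% for type 1 against at least 10% for type 2. The same paragraph calls the calculations conservative, on the ground that covariate adjustment will add precision.

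Other sections describe the two types very differently at baseline:

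- Section 4B, 4.2.1.2 says about "90% of youth with T2D were overweight or obese". It gives elevated blood pressure as 5.9% in type 1 and continues: "In contrast, 23.7% of adolescents with type 2 diabetes had elevated BP".
- Section 4B, 4.2.1.1.2 says elevated ACR "was 9.2% in youth with type 1 and 22.2% in type 2 diabetes".
- Section 6A, Table 6.2 gives BMI-z, mean (SD), as 0.6 (1.0) in type 1 and 2.1 (0.7) in type 2.

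**The concern.** An incidence comparison can use only people free of the condition at the start. Applying the pooled event-free share to each type assumes equal baseline prevalence in both, and the Protocol's own figures contradict that for obesity, blood pressure and ACR. The error falls on type 2, the small group that limits precision, and in those three rows it makes the group look larger than it is.

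Obesity is hit hardest. A count of 349 requires about three quarters of type 2 youth to be non-obese, while their mean BMI-z lies well above the obesity cut. Obesity is also the example the text uses to illustrate type 1 vs type 2 power. A reader of a null result would take it as coming from a comparison with 90% power.

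**Working it through.** **1. How Table 6-1 was built.** Divide each type 2 (14%) count by its row percentage: 423/0.92 = 459.8; 349/0.76 = 459.2; 262/0.57 = 459.6; 414/0.90 = 460.0; 418/0.91 = 459.3; 391/0.85 = 460.0. Each is 0.14 × 3,288 = 460, up to rounding. The pooled share was therefore applied to type 2 in every row. The type 1 obesity count gives 2069/0.76 = 2,722, which is 0.86 × the 3,166 used in 6.2.2, so the two columns rest on different totals.

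**2. Reproducing the stated 90%.** For rates p1, p2 and counts n1, n2, the continuity-corrected two-sided 5% test has power

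Φ{ [ |p1 − p2| − ½(1/n1 + 1/n2) − 1.96·s0 ] / s1 },

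where s0² = p̄(1 − p̄)(1/n1 + 1/n2), p̄ is the pooled rate, and s1² = p1(1 − p1)/n1 + p2(1 − p2)/n2.

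With 5% vs 10% and 2069/349: correction 0.00167, p̄ = 0.0572, s0 = 0.01344, s1 = 0.01676. Power = Φ[(0.05 − 0.00167 − 0.02634)/0.01676] = Φ(1.31) = 90.5%. The formula is sound and the printed power follows from the printed counts. The fault is in the type 2 count.

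**3. Type-specific event-free shares.**

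- Obesity, assuming normal BMI-z and a 95th-percentile cut of 1.645: type 2 Φ[(1.645 − 2.1)/0.7] = Φ(−0.65) = 25.8%; type 1 Φ[(1.645 − 0.6)/1.0] = 85.2%.
- Hypertension, with elevated blood pressure as proxy: type 2 76.3%, type 1 94.1%.
- ACR: type 2 77.8%, type 1 90.8%.

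Weighted 86/14, these come back close to the printed pooled inputs:

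- Obesity: 0.86 × 85.2 + 0.14 × 25.8 = 76.9% (printed 76%)
- Hypertension: 0.86 × 94.1 + 0.14 × 76.3 = 91.6% (printed 92%)
- ACR: 0.86 × 90.8 + 0.14 × 77.8 = 89.0% (printed 90%)

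**4. Corrected power, same 460 type 2 participants.** For obesity, 0.258 × 460 = 119 at risk. With 2069/119: correction 0.00444, p̄ = 0.0527, s0 = 0.02107, s1 = 0.02792. Power = Φ[(0.05 − 0.00444 − 0.04129)/0.02792] = Φ(0.15) = 56%. Raising the type 1 count to 0.852 × 2,722 = 2,319 changes this by less than one point.

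| Outcome | Type 2 at risk, printed | Type 2 at risk, type-specific | Rates | Stated power | Recomputed |
|---|---|---|---|---|---|
| Obesity | 349 | 119 | 5% vs 10% | 90% | 56% |
| Obesity | 349 | 119 | 10% vs 16% | 86% | 49–50% |
| Hypertension | 423 | 351 | 6% vs 10% | 80% | 74–75% |
| Hypertension | 423 | 351 | 12% vs 18% | 88% | 84% |
| ACR | 414 | 358 | 9% vs 15% | 93% | 90% |
| ACR | 414 | 358 | 19% vs 26% | 87% | 84% |

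The ranges reflect the choice of type 1 count.

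**5. Sensitivity, obesity 5% vs 10%.** Of 460 type 2 participants: 10% non-obese (46 at risk) gives 28%; 20% (92) gives 47–48%; 35% (161) gives 67%; 50% (230) gives 79–80%. With the 435 type 2 participants in Section 5B, Table 5-1 (107 + 328), 112 are at risk and power is 54%. With 119 at risk, 80% power needs a type 2 rate of about 12%, and 90% power about 14%.

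**The case against.** Several points on the other side have weight.

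- **The arithmetic is right.** The printed powers follow from the printed counts. This is a faulty planning input, not a miscalculation.
- **The tables are illustrative.** Section 6B presents its power material as selected examples, and eligibility is limited to people who already had a baseline visit (3,699 in Section 8B). No enrolment target depends on the obesity row. That lowers the stakes but does not make the stated power correct.
- **The 56% is model-based.** No non-obese percentage for type 2 is printed. The figure assumes normal BMI-z and borrows the registry mean and SD. The direction does not need normality: if the type 2 median lies above the cut, fewer than half are non-obese and power is at most about 80%.
- **Elevated blood pressure may not be defined as Table 6-1 defines hypertension**, and the type 2 figure is for adolescents. The hypertension correction is approximate.

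Two stronger readings are tempting. A reader might infer that type 2 counts are about three times too large throughout, or that Aim 1 as a whole is underpowered. The documents do not support either. The threefold excess (349/119 = 2.9) is in the obesity row only; it is about 1.2-fold for hypertension and ACR. In Research Question 1.1 obesity appears as a metabolic risk factor, not as one of the Aim 1 complications. A reader might also infer that continuous BMI should become the main adiposity comparison. That is a preference, and Table 6-4 already gives detectable BMI z-score differences using 450 type 2 participants.

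**Conclusion.** The point holds, and the 90% sentence is wrong as written. Scenario 1 of Table 6-1 assumes equal baseline prevalence in the two types, against the Protocol's own figures. The loss is large for obesity: about 56% instead of 90%, and about 50% instead of 86%. It is modest for hypertension and ACR, where only hypertension at 6% vs 10% drops below 80%. The obesity figures rest on normal BMI-z with a cut of 1.645 and on 460 type 2 participants; 20 to 35% non-obese gives 48 to 67% for 5% vs 10%, and no share up to 50% takes it above 80%. The LDL, hypoglycemia and DKA rows could move either way, because the document gives no type-specific baseline figures that match them. Calling the obesity comparison conservative is not tenable: precision from covariate adjustment is not shown to offset an at-risk group about one third of the size assumed.

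**What to change.** In Section 6B, 6.2.1:

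- Rebuild the Scenario 1 columns of Table 6-1 for all six outcomes, using event-free percentages by diabetes type from the SEARCH 1 and 2 baseline visits.
- Use one type 2 total throughout. The Protocol now uses about 460 (implied by Table 6-1), 450 (Table 6-4) and 435 (Table 5-1).
- Recompute the type 1 vs type 2 powers in Table 6-2.
- Replace the sentence claiming 90% power for incident obesity with the recomputed figure, or give the type 2 rate that would be detectable with 80% power.
- Remove the description of the calculations as conservative for that comparison.

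The cost is a tabulation of baseline data already collected, a recalculation and some rewording. Design, data collection and analysis methods do not change; some stated powers become less favourable.

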6.2.2. Prevalence Estimation

Unlike the incidence rate comparison, all SEARCH Cohort Study participants can be used for the prevalence rate analyses since the incident rate calculations need to remove participants who have the outcome present at visit 1 from the analyses. With this in mind we estimate that there will be 3166 participants available to contribute to prevalence rate estimates. Based on this, Table 6-3 shows a variety of scenarios for detectable differences comparing groups (i.e., type 1 vs type 2, non-Hispanic white vs others, etc) using a chi-square test to compare groups with alpha=0.05 (2-sided).

Table 6-3: Scenarios fo	or Detecting	Statistical Di	fferences	in Prevale	ence of Retinop	athy and		
Neuropathy								
Outcome	316/2849		473/2692		2112/1049 (Anticipated NHW			
				vs. Other Race Split)				
	Percentage with trait in smaller group							
	10%	20%	10%	20%	10%	20%		
	Detectable Difference (Power)							
Retinopathy	.16 (81)	.28 (86)	.15 (82)	.27 (89)	.14 (89)	.25 (88)		
	5%	15%	5%	15%	5%	15%		
Neuropathy	.10 (85)	.22 (83)	.09 (84)	.21 (85)	.08 (88)	.20 (93)		

Section 6B - Statistical Considerations (Phase 3 - 12/2010) Cohort Study

Based on this table, we see that there is 81% power to detect a difference between Type 1 and Type 2 participants on their prevalence of retinopathy: 10% in the Type 1 group and 16% or higher in the Type 2 group, a realistic potential comparison given early pilot findings of 18% of youth with evidence of DR among the first 38 evaluated.

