4.1. SEARCH COHORT STUDY OBJECTIVES

4.1.1. Goals

SEARCH is an on-going, multi-center, epidemiological study consisting of the largest and most culturally diverse population of youth with diabetes ever assembled. Initiated in 2000, SEARCH encompasses the major racial/ethnic groups in the U.S: non-Hispanic white (NHW), African-American (AA), Hispanic (H), Asian-Pacific Islander (API) and American Indian (AI). SEARCH was designed to estimate the prevalence and incidence of diabetes among youth, and to characterize diabetes-related health outcomes and their risk factors including barriers to care and quality of health care. However, critical questions remain regarding the impact of diabetes on the health outcomes of affected youth. In the SEARCH Phase 3 Cohort Study, we will conduct an in-person research visit with SEARCH participants whose diabetes was incident in 2002 or later, with duration of diabetes > 5 years who completed a baseline study visit (expected n=3699). SEARCH has a well-established and ongoing infrastructure and is uniquely positioned to successfully address the following Aims:

Aim 1: Assess the prevalence and incidence of, and risk factors for chronic microvascular (retinopathy, nephropathy, and autonomic neuropathy) and selected markers of macrovascular complications (hypertension, arterial stiffness) of diabetes.

Research Question 1.1: Is the presence and incidence of selected chronic complications and markers of complications different according to a) clinical diabetes type (Type 1 or Type 2 Diabetes); b) biochemical dimensions of diabetes type (autoimmunity, insulin sensitivity score, residual insulin secretion); or c) metabolic risk factors (hyperglycemia, hypertension, obesity, dyslipidemia, presence and severity of diabetic ketoacidosis at onset or thereafter)?

Research Question 1.2: Is the presence of risk factors for, and selected markers of, chronic complications associated with race/ethnicity or other socio-cultural factors (e.g., family structure, household income, or parental education)? Using data collected at previously study visit(s), what are associations of selected factors including physical inactivity, high fat diet, selected nutrient biomarkers (e.g., plasma vitamin D), cigarette smoking exposure, and depressive symptoms and these vascular markers?

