Aim 2: Assess the incidence of, and risk factors for, serious acute complications of diabetes including severe hypoglycemia and diabetic ketoacidosis (DKA).

Research Question 2.1: Does the incidence of serious acute complications differ according to biochemical dimensions of diabetes type (autoimmunity, insulin sensitivity score, residual insulin secretion), glycemic control or diabetes treatment regimen?

Research Question 2.2: Does the incidence of serious acute complications differ according to race/ethnicity or other socio-cultural factors (e.g., family structure, household income, or parental education)?

Aim 3: Determine the degree to which barriers to care, quality of care, and the process of transition from pediatric to adult health care impact disease factors, including dimensions of diabetes type, and diabetes-related outcomes (acute and chronic complications, quality of life, diabetes-related mortality).

Research Question 3.1: Do specific barriers to care and quality of care assessed early in the course of their diabetes effect a) the evolution of key dimensions of diabetes type; b) metabolic status (e.g., A1c, lipid profile, weight status); c) markers of acute and chronic complications of diabetes; or d) quality of life?

Research Question 3.2: Do specific barriers to care and quality of care explain differences in health outcomes experienced by minority youth, compared to their non-Hispanic white counterparts with the same type of diabetes (T1D or T2D)? Health outcomes will include dimensions of diabetes type, metabolic status, markers of acute and chronic complications, quality of life, and mortality.

Research Question 3.3: What are the specific barriers to care that emerge as youth with diabetes move into early adulthood (e.g., loss of or change in insurance; change in health care provider)? Do these barriers affect metabolic status and co-morbidities? Are these barriers more common among persons of minority race/ethnicity compared to NHW individuals, independent of other socio-cultural factors (e.g., family structure, household income, or parental education)?

Aim 4: Maintain and supplement the SEARCH repository for biological specimens, and promote access to SEARCH for conduct of scientifically and logistically appropriate ancillary studies.

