4.2.1.1. Health Status of Youth with Diabetes: Complications and Risk Factors

4.2.1.1.1. Acute Complications

The major acute complications of diabetes in youth are diabetic ketoacidosis (DKA) and hypoglycemia. Two European studies reported a frequency of DKA of between 21-26% ^(12, 13). In pediatric patients with established diabetes, the frequency of DKA ranged from 1-10 per 100 patient years ^(14, 15). Older age, higher HbA_{1c}, higher insulin doses, mental health diagnoses, and underinsurance were associated with higher risk of DKA ⁽¹⁵⁾. Youth with T2D may also present with DKA, with frequencies of 11-25% reported ⁽¹⁶⁻¹⁸⁾. They may also present with hyperglycemic hyperosmolar non-ketotic coma (HHNK) ⁽¹⁹⁾. SEARCH reported a similar frequency of DKA at diagnosis of 25.5% ⁽²⁰⁾.

Severe hypoglycemia occurs in 10-25% of children with diabetes each year ⁽²¹⁾. In addition, unrecognized hypoglycemia occurs commonly with up to 73% of hypoglycemic episodes occurring without detection by children or their parents ⁽²²⁾. Hypoglycemia unawareness, a condition more common in those with more intensive glycemic control, longer duration, and younger age of onset further increases the risk of severe hypoglycemia. Early evidence suggests that use of continuous subcutaneous insulin infusions (CSII) paired with continuous glucose monitoring (CGM) as a "closed loop artificial pancreas" was associated with a 57-80% decrease in nocturnal hypoglycemia ⁽²³⁾; however, the impact of new technologies on acute complications in diverse populations is not known. From SEARCH, we know that insulin treatment regimens impact the frequency of acute complications, with youth on CSII having fewer acute complications, including hospitalizations, than youth on other regimens ⁽²⁴⁾. SEARCH provides a large, multi-ethnic population of youth from diverse economic backgrounds with both T1 and T2D to address how acute complications are influenced by both the biochemical dimensions of diabetes type, race/ethnicity, other socio-cultural factors, and by health care and barriers to care. Findings will inform recommendations for diabetes management and health care delivery to reduce risk for acute complications.

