6.1. STATISTICAL ANALYTIC METHODS

6.1.1. Incidence Rate Estimation

Because all SEARCH Cohort Study participants will have had at least one previous SEARCH in-person visit, we will be able to define a group of participants who were free from the event of interest (i.e., normotensive) at "baseline". Multiple logistic regression methods will be employed to examine the incidence rates of binary measures (e.g., hypertension) of interest. Predictors can include categorical or continuous variables. A continuous variable that measures the time between visits for each participant (to account for the fact that individuals will have different lengths of follow-up) and the predictor- by-time interaction will be included. Next, we will expand the logistic regression model to include other participant level characteristics (e.g., SEARCH clinical center, age, and gender [a "demographically adjusted model"]). We will then expand the model to adjust for other covariates. In addition, we will examine potential interactions; if significant interaction is present, analyses will be performed stratified by that characteristic.

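### The Aim 2 incidence analysis drops participants with recent DKA or hypoglycemia although these events recur, and Table 6-2 plans on DKA rates above the range the protocol quotes

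*Protocol*

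**What the plan says.** Cohort Study Aim 2 (Section 4B, 4.1.1) reads "Assess the incidence of, and risk factors for, serious acute complications of diabetes including severe hypoglycemia and diabetic ketoacidosis (DKA".

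For incidence, Section 6B, 6.1.1 plans to "define a group of participants who were free from the event of interest" at baseline, gives normotension as its example, and then fits logistic regression to a binary outcome. Section 6.2.2 repeats the rule when it contrasts incidence with prevalence: "the incident rate calculations need to remove participants who have the outcome present at visit 1".

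Table 6-1 (6.2.1) carries the rule through to sample sizes. Alongside hypertension, obesity, LDL and ACR it has rows beginning "Hypoglycemia in last 6 months (91" and "DKA in last 6 months (85"; the number is the percentage free of the event at the initial visit. No separate at-risk rule is given for these two rows.

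Table 6-2 then states power for DKA in the last 6 months:
- Type 1 against type 2: 15% v 21% (81%) and 25% v 32% (80%).
- Non-Hispanic white (NHW) against other: 9% v 13% (87%) and 19% v 24% (84%).

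The background (Section 4B, 4.2.1.1.1) says that in pediatric patients with established diabetes "the frequency of DKA ranged from 1-10 per 100 patient years".

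**The concern.** Removing prevalent cases is right for a condition that, once present, cannot newly occur. DKA and hypoglycemia are episodes. The Executive Summary says DKA can occur at presentation or in established diabetes, and the neuropathy background in Section 4B refers to recurrent hypoglycemia. A participant with an episode before the initial visit can have another and belongs in the denominator.

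Under the stated rule, the Aim 2 incidence figure is conditional on having had no recent event. If recent events mark higher risk, that figure is too low for the cohort as a whole.

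The second issue concerns planning. Cohort members have had diabetes for at least 5 years at the visit (Section 5B, 5.1.1), so the established-diabetes rate is the natural comparator for the DKA rows of Table 6-2. If true rates lie in that range, the stated DKA power is not available for differences of the relative size shown.

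**Working it through.** **Numbers removed.** Section 6.2.2 gives 3,166 participants for prevalence.
- DKA: 0.15 × 3,166 ≈ 475 removed.
- Hypoglycemia: 0.09 × 3,166 ≈ 285 removed.
- Lifting the rule gives 1/0.85 = 1.18, or 18% more participants for DKA, and 1/0.91 = 1.10, or 10% more for hypoglycemia.

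**Direction of the bias.** Let the removed group have k times the risk of the rest. The retained-group rate, as a fraction of the whole-cohort rate, is 1/(0.85 + 0.15k) for DKA and 1/(0.91 + 0.09k) for hypoglycemia. The protocol gives no k, so these values are illustrations only.

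| k | DKA | Hypoglycemia |
|---|---|---|
| 1 | 1.00 | 1.00 |
| 2 | 1/1.15 = 0.87 | 1/1.09 = 0.92 |
| 3 | 1/1.30 = 0.77 | 1/1.18 = 0.85 |

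**Reproducing Table 6-2.** The test is a continuity-corrected chi-square, two-sided alpha 0.05, with Table 6-1 sizes of 2314/391 (type 1/type 2) and 1749/941 (NHW/other). With p̄ the pooled proportion and c = 0.5(1/n1 + 1/n2),

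power = Φ{ [ |p2 − p1| − c − 1.96·√(p̄(1−p̄)(1/n1+1/n2)) ] / √(p1(1−p1)/n1 + p2(1−p2)/n2) }.

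For 15% v 21%: p̄ = 0.1587 and c = 0.0015. The argument is (0.0600 − 0.0015 − 0.0392)/0.0219 = 0.88, so power is 81.2%. The other three DKA entries come to 80.3%, 87.7% and 84.5%, against 80%, 87% and 84% stated. The arithmetic is sound, so only the inputs are in question.

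**Quoted rate on the table's scale.** The 6-month risk is 1 − exp(−rate × 0.5).
- 1 per 100 patient-years: 0.5%.
- 10 per 100 patient-years: 4.9%.

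The planned base rates of 9, 15, 19 and 25% are 1.8, 3.1, 3.9 and 5.1 times the 4.9%. By −ln(1 − p)/0.5 they correspond to about 19, 33, 42 and 58 events per 100 patient-years.

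**Power at lower base rates.** This keeps the Table 6-1 sizes and the ratios of the first rows (21/15 = 1.40; 13/9 = 1.44). For 5% v 7%, p̄ = 0.0529 and the argument is (0.0200 − 0.0015 − 0.0240)/0.0137 = −0.40, so power is 34%.

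| 6-month base rate | Type 1 v type 2, ratio 1.40 | NHW v other, ratio 1.44 |
|---|---|---|
| as stated (15%; 9%) | 81% | 87% |
| 5% | 34% | 62% |
| 2.5% | 19% | 34% |
| 0.5% | 5% | 8% |

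**Ratio needed for 80% power.**

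| 6-month base rate | Type 1 v type 2 | NHW v other |
|---|---|---|
| 4.9% | 1.79 (8.7%) | 1.57 (7.7%) |
| 2.5% | 2.18 | 1.86 |
| 0.5% | 4.4 | 3.5 |

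**Effect of lifting the exclusion on power.** Dividing the sizes by 0.85 gives about 2722/460 and 2058/1107. The stated powers of 81, 80, 87 and 84% become 87, 86, 92 and 90%. At a 4.9% base the detectable ratios fall from 1.79 to 1.72 and from 1.57 to 1.52. The gain is modest; the main reason to lift the rule is the meaning of the estimate.

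**The case against.** **Aim 2 does not rest on the incidence analysis alone.** A reader might infer that the plan makes recurrence impossible to study. The opening of Section 6B also assigns Aim 2 to prevalence estimation and to longitudinal models. Neither removes anyone, and 6.1.3 allows GEE logistic or log-linear models for discrete outcomes. That objection stands, and it confines the point to the incidence analysis. It does not lift the rule there.

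**Onset DKA.** A reader might infer that the rule mainly removes youth who presented in DKA. That is an inference: the protocol does not say whether the 6-month item counts the onset episode. Nor does the wording "presence and severity of diabetic ketoacidosis at onset or thereafter" help. It belongs to Research Question 1.1 on chronic complications, where these youth stay in the analysis because removal is outcome by outcome.

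**Status of the quoted range.** The 1-10 per 100 patient-years is a background literature figure, not a planning assumption, and Table 6-2 presents scenarios. This is fair. But it is the only rate for DKA in established diabetes that the protocol gives, and no source is shown for the higher ones. The footnote about rates observed in SEARCH 1 and 2 is marked only on the hypertension entries. Table 6-1 does show 15% with DKA at the initial visit, but that visit came earlier in the disease than the cohort visit.

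**Other readings.** If the Table 6-2 rates were cumulative over follow-up, the comparison would change, but the row label says the last 6 months. A reader might also call the two scenarios contradictory because they imply different overall rates. That treats detectable thresholds as predictions. Nor does the rate criticism extend to hypoglycemia: the quoted 10-25% a year for severe events is about 5.1-13.4% per 6 months, and the base rates of 11-33% are 0.8 to 2.5 times the top of that.

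**Conclusion.** The point holds in two separate parts.

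1. The first-event rule is misapplied to DKA and hypoglycemia in the incidence analysis. It excludes about 15% and 9% of participants who are still at risk. That the estimate is too low is probable rather than shown, because it assumes that a recent event marks higher risk. The exclusion covers only the 6 months before the initial visit, not all earlier events.

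2. The DKA rows of Table 6-2 use base rates 1.8 to 5.1 times the top of the only established-diabetes range in the protocol. The excess is largest for the three rates of 15% and above; the 9% rate is less than twice the top. Even near the top of the range, power for the table's own ratios is 34% and 62%, not 81% and 87%, and 80% power needs ratios of about 1.8 and 1.6. This assumes that the quoted range applies to the cohort and that the row label's 6-month window is meant. Observed SEARCH 6-month rates at comparable duration, if they support the current figures, would answer this part.

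**What to change.** - In 6.1.1 and 6.2.2, limit the visit-1 exclusion to lasting conditions. For DKA and hypoglycemia, analyse all participants with outcome data and enter the event in the 6 months before the initial visit as a covariate. Keep a first-event analysis as secondary if wanted.
- In Table 6-1, replace the at-risk sizes in these two rows with the full sample (about 3,166).
- In Table 6-2, restate the DKA rows at rates consistent with the quoted 1-10 per 100 patient-years, or document the observed SEARCH 6-month rates that justify the present ones.
- Modelling event counts is optional. It depends on counts being collected, and Section 5B, 5.1.10 says only that DKA occurrence is recorded, as an emergency department visit or a hospitalization.

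The cost is a few sentences and recalculated table rows, with no new data collection.
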